7.7.3 Vital Signs

Vital signs (weight, pulse rate, systolic blood pressure, diastolic blood pressure, and temperature) will be summarized and listed. The summaries include:

- Observed values
- Change from baseline by scheduled visit (including mean, median, standard deviation, maximum, and minimum)
- Percentage change from baseline at each scheduled visit through treatment discontinuation

7.7.4 Analyses of ECG Change

ECG parameter will be summarized by test and by visit. Summary statistics for the change from baseline at end-of-treatment (EOT), where end-of-treatment will be summarized using the last non-missing post-baseline result no more than 45 days after treatment discontinuation or initiation of subsequent therapy (whichever is first, if applicable), will be tabulated. In the case of multiple assessments at a visit, baseline will

be the last value prior to dosing. Observed values, change from baseline, and percent change from baseline at each scheduled visit and EOT in parameter results will be summarized. One-sided 95% confidence interval for the change from baseline will be provided for each visit.

The QTcF triplicate will be summarized and tabulated by maximum QTcF (msec) increase from baseline and QTcF (msec) value at any time during treatment:

- Maximum QTcF (msec) increase from baseline on treatment:
 - $\Delta\text{QTcF} > 10$ msec
 - $\Delta\text{QTcF} > 20$ msec
 - $\Delta\text{QTcF} > 30$ msec
 - $\Delta\text{QTcF} > 60$ msec
- QTcF on treatment:
 - $\text{QTcF} > 450$ msec
 - $\text{QTcF} > 480$ msec
 - $\text{QTcF} > 500$ msec

7.7.5 Echocardiography

The presence of pericardial effusion will be summarized using the shift table at each scheduled visit.

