2.2.3 Safety Endpoints

- Adverse Events
- Vital signs
- Laboratory abnormalities
- Electrocardiographic intervals (e.g. QTc)
- Echocardiography
- Components of a fluid retention questionnaire

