5.5 Management of Adverse Reactions

5.5.1 Management of Serosal Effusions

Serosal effusions (pleural or pericardial, or ascites) have been observed with rovalpituzumab tesirine, alone or in combination with peripheral edema and/or hypoalbuminemia. These events have the potential to be life-threatening (e.g. pericardial tamponade). Therefore, development of any of these events or worsening from baseline warrants prompt evaluation by the Investigator or

designee. Alternative causes, such as infection, congestive heart failure, or disease progression, should be ruled out.

In the event of a grade 2 or higher AE in this group (effusions, edema, hypoalbuminemia) considered related to rovalpituzumab tesirine:

- Systemic corticosteroids, when initiated promptly, have been reported to be beneficial in some prior cases. Consider a tapering regimen, such as dexamethasone up to 8 mg orally twice a day for 5 days, followed by 4 mg orally twice a day for 5 days, then 2 mg orally twice a day for 5 days. Alternatively, nonsteroidal therapies for serositis may be considered, such as non-steroidal anti-inflammatory drugs (NSAIDs, e.g., ibuprofen 400-600 mg orally three to four times daily) or colchicine (e.g. 0.6 mg orally two to three times daily) given for 1-2 weeks.
- Until clinical experience suggests otherwise, guidance for dose delay and/or reduction, as well as criteria for ongoing dosing, should follow Sections [5.2.2](#) and [5.2.3](#).

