6.3.2 Day 1 (± 2 days for Cycle 2 and Beyond)

If Screening Visit activities occur within 1 day prior to Cycle 1, Day 1, the following pre-dose assessments do not need to be repeated at the Cycle 1, Day 1 visit: physical examination, ECOG performance status, and local safety labs (complete blood count, chemistries, coagulation tests, urinalysis, pregnancy test; if obtained within 1 calendar day).

Day 1 procedures may be performed within 1 calendar day prior to dosing of study drug. Results from local clinical laboratory tests (at least CBC with differential and chemistry panel) must be available prior to dose.

- Physical examination (see Section [7.6.2](#))
- Vital signs – within 30 minutes prior to the infusion, and then post-infusion at 30 minutes (± 10 minutes), 2 hours (± 15 minutes) and 4 hours (± 30 minutes; see Section [7.6.3](#))
- Complete blood count (see Section [7.6.4](#))
- Chemistry Panel (see Section [7.6.4](#))
- Coagulation tests (see Section [7.6.4](#))
- Urinalysis (see Section [7.6.4](#))
- Pregnancy test (see Section [7.6.4](#)) for women of child-bearing potential
- Triplicate ECG - prior to and after the infusion (see Section [7.6.5](#))
- Echocardiogram (see Section [7.6.6](#))
- ECOG performance status (Appendix [12.2](#))
- Fluid retention questionnaire (see Section [7.6.8](#))
- Blood sample for pharmacokinetics – 

- Blood sample for anti-therapeutic antibodies
- Blood inflammatory markers (see Section [7.4.2](#))
- Blood tumor markers (see Section [7.4.3](#))
- Soluble biomarkers (see Section [7.4.4](#))
- 
- Subjects will take dexamethasone 8 mg PO twice a day (the first dose of the day should be at least 30 minutes, but no more than 4 hours, prior to the rovalpituzumab tesirine dose)
- Administration of rovalpituzumab tesirine (see Section [5.1](#))

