7.6.6 Echocardiogram

Echocardiograms will be performed at the indicated times to assess any pericardial effusions, if present, as well as cardiac function (left ventricular ejection fraction, LVEF).

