7.7.6 ECOG Performance Status

ECOG scores will be summarized using the shift table at each scheduled visit and listed. Maximum shift of ECOG performance status from baseline will also be summarized.

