- 14) Hepatitis B and C tests include Hep B surface antigen (HBsAg), Hep B core antibody (HBcAb) and HCV antibody. Results that may be consistent with chronic or active infection must be confirmed by PCR tests for Hep B and/or C.
- 15) Pregnancy test consists of blood or urine testing for beta-human chorionic gonadotropin (β -hCG) for women of child-bearing potential. Additional testing may be done per the investigator.
- 16) ECG consists of a 12-lead study taken in triplicate. For Day 3 assessment, evaluate ECGs at approximately the same time of day as on Day 1 - prior to blood sample for pharmacokinetics.
- 17) Echocardiogram includes assessment of left ventricular ejection fraction (LVEF) and pericardial effusion.
- 18) Fluid Retention Questionnaire includes queries of daily weights and worsening or new edema or dyspnea.
- 19) Subjects will maintain a diary of daily weights.
- 20) Concomitant Therapies include names of all concomitant medications, blood products, procedures and radiotherapy, including dates of administration, dose regimen, route of administration, and purpose.

21) Every 6 weeks until 6 months, then every 12 weeks, until disease progression or initiation of new anticancer therapy. Thereafter, Disease/Response Assessment consists of subsequent anticancer therapies and dates, date of progression (if not already captured on study), and survival status.

22) May be omitted if a Disease/Response Assessment was performed within the preceding 6 weeks.

23) CT imaging of the chest, abdomen, and pelvis, and neck (if indicated), for assessment via RECIST v1.1.

24) MRI of the brain is only required during treatment when clinically indicated (e.g. if CNS progression is documented)

25) Paraneoplastic assessment includes documentation of the presence of a SCLC-related paraneoplastic syndrome, if present.

26) [REDACTED]

27) Tumor Tissue consists of procurement for DLL3 testing of archived, representative tumor tissue, or an optional fresh tumor biopsy, if accessible. With consent from the subject, tumor tissue may be obtained prior to the screening period and tested for DLL3 expression. Optional: collection of tumor tissue at progression to better understand mechanisms of resistance and expression of DLL3.

28) [REDACTED]

29) [REDACTED]

30) [REDACTED]

31) [REDACTED]

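### The only planned echocardiography summary is presence of pericardial effusion at scheduled visits, with no worst post-baseline shift, no severity category and no summary of LVEF

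*SAP*

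**What the plan says.** Both documents list echocardiography as a safety endpoint (Protocol 2.2.3, SAP 4.5) without naming its components. Protocol 7.6.6 says the examination is done "to assess any pericardial effusions, if present, as well as cardiac function (left ventricular ejection fraction, LVEF"). Note 17 to the schedule in SAP Appendix B agrees: "Echocardiogram includes assessment of left ventricular ejection fraction (LVEF) and pericardial effusion".

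Scheduled echocardiograms fall on Day 1 of each cycle (Protocol 6.3.2) and at the End of Treatment visit (Protocol 6.4). For effusions, edema and hypoalbuminemia, Protocol 5.5.1 adds that "development of any of these events or worsening from baseline warrants prompt evaluation by the Investigator" or a designee, so work-up outside the schedule is foreseen.

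The analysis is SAP 7.7.5: "The presence of pericardial effusion will be summarized using the shift table at each scheduled visit". One table matches it, 14.3_7.1, whose title names pericardial effusion only. Protocol 9.2.9.3 plans no echocardiography analysis. The next SAP section, 7.7.6, starts from the same kind of by-visit shift table for ECOG and then adds: "Maximum shift of ECOG performance status from baseline will also be summarized".

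**The concern.** The protocol describes serosal effusions as a notable toxicity of this drug (1.1.3) and as potentially life-threatening through tamponade (5.5.1). Echocardiography is the direct measurement of the pericardial form. A yes/no shift at a few fixed visits is a coarse summary of it, for three reasons:

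- It takes in only what is present on the scheduled day.
- It cannot separate a small effusion from a large one.
- It leaves out the second quantity that the examination measures, LVEF.

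A reader of the study report who turned to the echocardiography table for the effusion findings could therefore see fewer and milder ones than the echocardiograms recorded. That reader would also find no summary of ventricular function.

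**Working it through.** The plan gives no figure to reproduce. The check is a count of visits and a comparison of passages.

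**Scheduled echocardiograms, initial course.** Day 1 procedures precede dosing (Protocol Appendix 12.1, note 2), so the Cycle 1 Day 1 echocardiogram is the baseline. Cycle 2 Day 1 is about 42 days later. End of Treatment is 42 ± 3 days after the last dose, or within 7 days of the decision to discontinue if that is later.

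- Two doses: 3 scheduled − 1 baseline = 2 post-baseline points, at about day 42 and day 42 + 42 = 84 after the first dose.
- One dose: 2 scheduled − 1 baseline = 1 post-baseline point (End of Treatment).

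**What Table 14.3_7.1 would show**, taking presence as yes/no:

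| Course | Entry in 14.3_7.1 | Where else it could appear |
|---|---|---|
| No baseline effusion; one found on an unscheduled echocardiogram and resolved or drained before the next scheduled one | Absent to absent | AE tables if reported; listing |
| No baseline effusion; fatal effusion before the next scheduled echocardiogram | No entry after onset | AE, SAE and death tables; listing if imaged |
| Small baseline effusion, larger later | Present to present | AE tables if reported; listing if size is recorded |
| Treatment stopped, effusion still present at End of Treatment | Absent to present | Shown correctly |
| Fall in LVEF | Not in the table | AE tables if clinically significant; possibly the listing |

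**Comparison with other safety measures in the SAP.** Laboratory tests have a shift to maximum post-baseline grade, and the largest-change table takes in unscheduled visits (7.7.2). QTcF has a maximum increase on treatment (7.7.4). ECOG has a maximum shift (7.7.6, Table 14.3_8.1). Echocardiography has no worst or any-time summary.

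**Does SAP 9 fill the gap?** Its default is tabulation by scheduled visit. It then allows unscheduled visits to supply the baseline, the last post-baseline value and the maximum change in shift tables. SAP 7.7.5 asks for neither a last value nor a maximum, so apart from setting the baseline the rule has nothing to act on.

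**Severity.** Protocol Appendix 12.5 separates small-to-moderate asymptomatic pericardial effusion (Grade 2) from physiologic consequences (Grade 3) and life-threatening consequences (Grade 4). A presence table cannot carry that distinction.

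**LVEF.** In the SAP text available it appears only in schedule note 17. No LVEF table or figure is in the Appendix G list.

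**The case against.** The strongest reply is that the safety analysis does not rest on this table, and most of that reply stands. A symptomatic effusion is clinically significant or needs intervention, so it is recordable as an AE, as is worsening of a baseline condition (Protocol 7.6.1.1). Such events feed TEAE tables by preferred term and grade, and the SAE, discontinuation and death tables (SAP 7.7.1, Appendix G). Tamponade would be an SAE reportable within 24 hours. There is an AESI summary whose search terms are blacked out, so no one can say that effusion is missing from it. A by-subject echocardiogram listing is also planned.

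A reader might therefore infer too much in two ways:

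- **That these effusions go unreported in the trial.** The documents do not support this. The gap is in the echocardiography summary.
- **That subjects who stop treatment have no chance of a positive scheduled echocardiogram.** Protocol 6.4 gives them an End of Treatment visit that includes one. The table misses only what has gone before that visit, or deaths before it.

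The AE route still does not replace the endpoint. Abnormal diagnostic findings are generally not AEs unless they are clinically significant, need intervention, are serious, or affect treatment or study participation (Protocol 7.6.1.1). An asymptomatic enlargement or LVEF fall may never become one. Protocol 7.6.1.3 ends routine AE collection 30 days after the last dose, about 42 − 30 = 12 days before End of Treatment (9 to 15 days over the ± 3-day window). The schedule in Appendix 12.1 appears to run collection to End of Treatment if that is later. Under the shorter period, a non-serious effusion found and gone in that interval could miss both sets of tables. A listing is also not a summary.

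Two further limits are fair. Protocol 5.5.1 asks for prompt evaluation without naming an echocardiogram. And no passage shows whether the echocardiogram CRF holds effusion size.

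**Conclusion.** The point holds for the echocardiography summary and no further. As written, SAP 7.7.5 and Table 14.3_7.1 cannot show between-visit effusions that resolve, are drained or are fatal, or worsening of an existing effusion. LVEF is collected and not summarised. The relation between 7.7.5 and SAP 9 is unclear rather than an outright exclusion of unscheduled data, but nothing in 7.7.5 brings those data in.

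The size cannot be given as a percentage. The documents contain no rate of effusion, of baseline effusion or of detection between visits. What can be stated is the sparse sampling: at most two post-baseline points about six weeks apart, or one after a single dose. The conclusion assumes that presence is coded yes/no, as the wording implies, and that unscheduled echocardiograms are recorded when done.

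Severity is minor. The display is descriptive, with no formal inference planned (SAP 7.7), and neither the response rate nor overall survival is affected. It merits correction because the endpoint is named, the toxicity is potentially life-threatening, and comparable measures already have the missing summary.

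**What to change.** In SAP 7.7.5 and Appendix G:

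1. Keep the by-visit table.
2. Add a shift from baseline to worst post-baseline effusion status over all scheduled and unscheduled echocardiograms in the treatment period. State that this is the maximum shift to which SAP 9 applies, as for ECOG.
3. Use effusion size categories only if the echocardiogram CRF records them. Otherwise use presence, and cross-reference the graded AE table. CTCAE grade is an AE severity and should not be presented as an echocardiogram reading.
4. Add LVEF observed value and change from baseline by visit, and lowest post-baseline LVEF.

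The cost is one or two extra descriptive tables. No new procedure is needed, and because no principal feature changes, Protocol 9.2 would not call for an amendment. The reported effusion rate may be higher than under the by-visit table alone, and a footnote should say that unscheduled examinations are included.

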7.7.6 ECOG Performance Status

ECOG scores will be summarized using the shift table at each scheduled visit and listed. Maximum shift of ECOG performance status from baseline will also be summarized.

7.7.7 Concomitant Medications

World Health Organization (WHO) Drug Dictionary will be used for coding medication terms. Medications taken prior to the first dose of study medication through 30 days following the last dose of study medication or medications taken after the first dose of study medication through 30 days following the last dose of study medication will be considered as concomitant medications, which will be listed and summarized (frequency and percentage of subjects) by preferred name. Subjects will be counted once per each unique medication.

7.8 Analysis of Pharmacokinetic, Pharmacodynamic, and Biomarker Endpoints

Pharmacokinetic Endpoints

Rovalpituzumab tesirine ADC concentrations will be listed by patient and summarized descriptively (arithmetic mean, standard deviation, minimum, median, maximum). Concentrations below the lower limit of quantification of the assay will be treated as missing. Results of the population PK analysis, including rovalpituzumab tesirine pharmacokinetic parameters (e.g. Cmax, AUC), will be reported separately.

Pharmacodynamic and Biomarker Endpoints

Summary statistics will be generated for tumor expression of DLL3 in dosed subjects. Exploratory analyses of other pharmacodynamics and biomarker endpoints (e.g. inflammatory markers, blood tumor markers, [REDACTED] soluble DLL3) may be performed if deemed necessary and appropriate.

8. INTERIM ANALYSIS

An interim analysis will be conducted when at least one post-baseline response assessment from 60 evaluable subjects with DLL3 high expression per IHC assay specification are available. Evaluable subjects will be those who have measurable disease per central reader with at least one post-baseline response assessment, which can include the response assessment performed at the end of treatment study visit. This interim analysis will be used to determine if there is sufficient response as described in Section 3.1.

An independent Data Monitoring Committee (iDMC) will be formed to review the efficacy and safety data periodically and provide recommendations. Detailed information regarding the composition of the iDMC and detailed iDMC procedures will be provided in a separate charter maintained by the sponsor and/or designee. The iDMC will review the efficacy and safety data periodically and provide recommendations according to the charters. The iDMC will review safety data approximately every 6 months. The iDMC may request further safety analyses.

9. VISIT WINDOWS

Efficacy analyses based on response assessment will include all scans, including those from unscheduled visits. All data will be tabulated according to scheduled visits, unless otherwise specified. No visit windows will be developed for the safety analysis of this study. Unscheduled visits will be used to determine baseline, the last post-baseline value, maximum change from baseline in shift tables, or determination of response.

Response Assessment	Disease/Response Assessment ²¹	X										X ²²	X ²³
	MRI of the Brain		X									X ²⁴	X ²⁴
	Paraneoplastic Assessment ²⁵	X											

	Screening	Every Treatment Cycle							EOT ¹	LTFU			
		Day -14 to -1	-1	1 ²	2	3	8	15	22	29	36	≤ 7 days prior to next dose	42 days after last dose
Day	Window	-	-	± 2d ²	-	± 1d	± 2d	± 2d	± 2d	± 3d	± 3d	± 3d	± 1w

Table Notes

- 1) EOT occurs 42 ± 3 days after last dose, or within 7 days of documentation of the decision to discontinue treatment, whichever is later.
- 2) Day 1 procedures should be performed prior to dosing of study drug (within 1 day); results from local clinical laboratory tests must be available prior to dose; ± 2 d window for Cycle 2 Day 1 and beyond
- 3) Days 36–42 of each cycle.
- 4) Follow-up occurs every 6 weeks until 6 months, then every 12 weeks. See Section 6.5 of the protocol
- 5) Informed consent will be obtained prior to the performance of any study procedures and may occur within 30 days of the Day 1 visit. Screening assessments will be completed within 14 days of the Day 1 visit.
- 6) Medical and Surgical History includes descriptions of conditions or procedures, and dates of onset - offset.
- 7) Malignancy History includes tumor type, stage, sites of metastases, mutational status.
- 8) Prior Anticancer Treatments include names of specific treatments, dates of administration, response to therapy, and duration of response, if known
- 9) Vital signs include temperature, blood pressure, pulse, respirations, and weight.
- 10) Complete Blood Count includes white blood cell count with five-part differential (neutrophils, lymphocytes, monocytes, eosinophils, and basophils), red blood cell count, platelet count, hemoglobin, and hematocrit.
- 11) Chemistries include electrolytes (sodium, potassium, chloride, and carbon dioxide), creatinine, blood urea nitrogen (BUN), estimated glomerular filtration rate, glucose, albumin, total protein, liver function tests (total and direct bilirubin, ALT, AST, alkaline phosphatase, lactate dehydrogenase), amylase, and lipase.
- 12) Coagulation tests include prothrombin time (PT), partial thromboplastin time (PTT), and international normalized ratio (INR)
- 13) Urinalysis includes dipstick results for color, appearance, specific gravity, pH, glucose, bilirubin, ketones, occult blood, and protein, as well as spot urine protein and creatinine.
- 14) Hepatitis B and C tests include Hep B surface antigen (HBsAg), Hep B core antibody (HBcAb) and HCV antibody. Results that may be consistent with chronic or active infection must be confirmed by PCR tests for Hep B and/or C.
- 15) Pregnancy test consists of blood or urine testing for beta-human chorionic gonadotropin (β -hCG) for women of child-bearing potential. Additional testing may be done per the investigator.
- 16) ECG consists of a 12-lead study taken in triplicate. For Day 3 assessment, evaluate ECGs at approximately the same time of day as on Day 1 - prior to blood sample for pharmacokinetics.
- 17) Echocardiogram includes assessment of left ventricular ejection fraction (LVEF) and pericardial effusion.
- 18) Fluid Retention Questionnaire includes queries of daily weights and worsening or new edema or dyspnea.
- 19) Subjects will maintain a diary of daily weights.
- 20) Concomitant Therapies include names of all concomitant medications, blood products, procedures and radiotherapy, including dates of administration, dose regimen, route of administration, and purpose.

21) Every 6 weeks until 6 months, then every 12 weeks, until disease progression or initiation of new anticancer therapy. Thereafter, Disease/Response Assessment consists of subsequent anticancer therapies and dates, date of progression (if not already captured on study), and survival status.

22) May be omitted if a Disease/Response Assessment was performed within the preceding 6 weeks.

23) CT imaging of the chest, abdomen, and pelvis, and neck (if indicated), for assessment via RECIST v1.1.

24) MRI of the brain is only required during treatment when clinically indicated (e.g. if CNS progression is documented)

25) Paraneoplastic assessment includes documentation of the presence of a SCLC-related paraneoplastic syndrome, if present.

26) [REDACTED]

27) Tumor Tissue consists of procurement for DLL3 testing of archived, representative tumor tissue, or an optional fresh tumor biopsy, if accessible. With consent from the subject, tumor tissue may be obtained prior to the screening period and tested for DLL3 expression. Optional: collection of tumor tissue at progression to better understand mechanisms of resistance and expression of DLL3.

28) [REDACTED]

29) [REDACTED]

30) [REDACTED]

31) [REDACTED]

32) Serosal Fluid entails procurement, where feasible, of any pericardial, pleural and/or ascitic fluid collected as part of routine care (e.g. as part of a therapeutic thoracentesis, pericardiocentesis, or paracentesis), for possible pharmacokinetic, pharmacodynamic and/or biomarker testing.

C. RANDOMIZATION ALGORITHM

Not Applicable

D. SAS ROUTINES

Endpoint	Test	SAS Code
ORR, CBR	95% Exact confidence interval for the proportion calculated using the exact binomial method	[REDACTED]
PFS, OS,	Kaplan-Meier method and 95% confidence interval for median calculated using the complementary log-log transformation	[REDACTED]

E. POTENTIALLY CLINICALLY SIGNIFICANT LABORATORY VALUES CRITERIA

No potentially clinically significant lab values criteria except the ones identified in section 7.6.2 were identified. The following normal ranges were used to identify values classified as High or Low.

Laboratory Test	Standard Result Unit	Normal Range Low	Normal Range High
Albumin	g/dL	3.5	5
Alkaline Phosphatase	U/L	30	120
ALT (SGPT)	U/L	10	40
AST (SGOT)	U/L	10	30
Basophils	10 ⁹ /L	0	0.2
Total Bilirubin	mg/dL	0.292	1.228
Blasts	%	0	0
Blood Urea Nitrogen	mmol/L	2.9	8.2
Calcium	mg/dL	8.2	10.2
Chloride	mmol/L	96	106
Carbon Dioxide	mmol/L	20	28
Serum Creatinine	mg/dL	0.6	1.2
Eosinophils	10 ⁹ /L	0	0.45
Glucose	mg/dL	70	110
Hematocrit	%	41	50
Hemoglobin	g/dL	14	17.5
Potassium	mmol/L	3.5	5
Lactate Dehydrogenase	U/L	100	200
Lymphocytes	10 ⁹ /L	1	4.8
Monocytes	10 ⁹ /L	0	0.8
Neutrophils	10 ⁹ /L	1.8	7.8
Platelets	10 ⁹ /L	150	350
Total Protein	g/dL	6	8
Sodium	mmol/L	136	142
WBC	10 ⁹ /L	4.5	11

F. ADVERSE EVENTS OF SPECIAL

Specific treatment-emergent adverse events of special interest (AESI) will be identified by the following search criteria:

Adverse Event of Special Interest

MedDRA Search Criteria / Codes

G. PLANNED TABLES, FIGURES AND LISTINGS

Table of Contents

TABLE 14.1_1.1 Disposition

TABLE 14.1_1.2 Analysis Populations

TABLE 14.1_1.3 Protocol Deviations

TABLE 14.1_2.1 Demographic Characteristics

TABLE 14.1_2.2 Baseline Characteristics

TABLE 14.1_2.3.1 Disease History

TABLE 14.1_2.3.2 Prior Therapies

TABLE 14.1_2.3.3 Medical History by System Organ Class and Preferred Term

TABLE 14.1_3.1 Treatment Exposure During Initial Treatment

TABLE 14.1_3.2 Dose Modification During Initial Treatment

TABLE 14.2_1.1 Best Response During Initial Treatment

TABLE 14.2_1.2.1 Best Response During Initial Treatment by Current Line of Therapy of 3L and 3L+

TABLE 14.2_1.2.2 Best Response During Initial Treatment by Current Line of Therapy of 3L and 3L+ and by Onset of Response

TABLE 14.2_1.2.3 Best Response During Initial Treatment by Current Line of Therapy of 3L and >4L

TABLE 14.2_1.3.1 Best Response During Initial Treatment by Response to Frontline Therapy of Sensitive, Resistant, and Refractory

TABLE 14.2_1.3.2 Best Response During Initial Treatment by Response to Frontline Therapy of Sensitive and Resistant/ Refractory

TABLE 14.2_ 1.4 Best Response During Initial Treatment by Current Line of Therapy of 3L and 3L+

TABLE 14.2_ 1.5 Concordance of Best Overall Response Between Investigator and Central Radiology Review Assessment

TABLE 14.2_ 1.6 Concordance of Objective Response Between Investigator and Central Radiology Review Assessment

TABLE 14.2_ 2.1 Overall Survival

TABLE 14.2_ 2.2.1 Overall Survival by Current Line of Therapy of 3L and 3L+

TABLE 14.2_ 2.2.2 Overall Survival by Subgroups

TABLE 14.2_ 2.2.3 Overall Survival by Response Subgroups

TABLE 14.2_ 2.2.4 Overall Survival by DLL3 for All Dosed Subjects

TABLE 14.2_ 3.1.1 Duration of Response During Initial Treatment

TABLE 14.2_ 3.1.2 Duration of Response During Initial Treatment by Current Line of Therapy of 3L and 3L+

TABLE 14.2_ 3.1.3 Duration of Response During Initial Treatment by Current Line of Therapy of 3L and 3L+

TABLE 14.2_ 3.2.1 Duration of Clinical Benefit During Initial Treatment

TABLE 14.2_ 3.2.2 Duration of Clinical Benefit During Initial Treatment by Current Line of Therapy of 3L and 3L+

Modified Intent-to-Treat Population

TABLE 14.2_ 3.2.3 Duration of Clinical Benefit During Initial Treatment by Current Line of Therapy of 3L and 3L+

TABLE 14.2_ 3.3.1 Progression-Free Survival During Initial Treatment

TABLE 14.2_ 3.3.2 Progression-Free Survival During Initial Treatment by Current Line of Therapy of 3L and 3L+

Modified Intent-to-Treat Population

TABLE 14.2_ 3.3.3 Progression-Free Survival During Initial Treatment by Current Line of Therapy of 3L and 3L+

TABLE 14.3_ 1.1.1 Summary of Treatment-Emergent Adverse Events During Initial Treatment

TABLE 14.3_ 1.1.2 Summary of Treatment-Emergent Drug-Related Adverse Events During Initial Treatment

TABLE 14.3_ 1.2.1 Incidence of Treatment-Emergent Adverse Events by System Organ Class and Preferred Term During Initial Treatment

TABLE 14.3_ 1.2.2 Incidence of Treatment-Emergent Adverse Events by Preferred Term During Initial Treatment

TABLE 14.3_ 1.2.3 Incidence of Treatment-Emergent Adverse Events by System Organ Class, Preferred Term, and Grade During Initial Treatment

TABLE 14.3_ 1.3.1 Incidence of Treatment-Emergent Drug-Related Adverse Events by System Organ Class and Preferred Term During Initial Treatment

TABLE 14.3_ 1.3.2 Incidence of Treatment-Emergent Drug-Related Adverse Events by System Organ Class, Preferred Term, and Grade During Initial Treatment

TABLE 14.3_2.1.1 Incidence of Treatment-Emergent Serious Adverse Events by System Organ Class and Preferred Term During Initial Treatment

TABLE 14.3_2.1.2 Incidence of Treatment-Emergent Serious Adverse Events by System Organ Class, Preferred Term, and Grade During Initial Treatment

TABLE 14.3_2.2.1 Incidence of Treatment-Emergent Drug-Related Serious Adverse Events by System Organ Class and Preferred Term During Initial Treatment

TABLE 14.3_2.2.2 Incidence of Treatment-Emergent Drug-Related Serious Adverse Events by System Organ Class, Preferred Term, and Grade During Initial Treatment

TABLE 14.3_2.3.1 Incidence of Treatment-Emergent Adverse Events Leading to Study Drug Discontinuation by System Organ Class and Preferred Term During Initial Treatment

TABLE 14.3_2.3.2 Incidence of Treatment-Emergent Adverse Events Leading to Treatment Interruption by System Organ Class and Preferred Term During Initial Treatment

TABLE 14.3_2.3.3 Incidence of Treatment-Emergent Adverse Events Leading to Dose Reduction by System Organ Class and Preferred Term During Initial Treatment

TABLE 14.3_2.3.4 Incidence of Treatment-Emergent Drug-Related Adverse Events Leading to Study Drug Discontinuation by System Organ Class and Preferred Term During Initial Treatment

TABLE 14.3_2.3.5 Incidence of Treatment-Emergent Drug-Related Serious Adverse Events Leading to Study Drug Discontinuation by System Organ Class and Preferred Term During Initial Treatment

TABLE 14.3_2.4.1 Incidence of Treatment-Emergent Adverse Events Leading to Death by System Organ Class and Preferred Term During Initial Treatment

TABLE 14.3_2.8.1 Incidence of Treatment-Emergent Adverse Events by System Organ Class, Preferred Term, and Gender During Initial Treatment

TABLE 14.3_2.8.2 Incidence of Treatment-Emergent Serious Adverse Events by System Organ Class, Preferred Term, and Gender During Initial Treatment

TABLE 14.3_2.8.3 Incidence of Treatment-Emergent Drug-Related Adverse Events by System Organ Class, Preferred Term, and Gender During Initial Treatment

TABLE 14.3_2.8.4 Incidence of Treatment-Emergent Drug-Related Serious Adverse Events by System Organ Class, Preferred Term, and Gender During Initial Treatment

TABLE 14.3_2.8.5 Incidence of Treatment-Emergent Adverse Events Leading to Study Drug Discontinuation by System Organ Class, Preferred Term, and Gender During Initial Treatment

TABLE 14.3_2.8.6 Incidence of Treatment-Emergent Adverse Events Leading to Death by System Organ Class, Preferred Term, and Gender During Initial Treatment

TABLE 14.3_2.9.1 Incidence of Treatment-Emergent Adverse Events by System Organ Class, Preferred Term, and Age Group During Initial Treatment

TABLE 14.3_2.9.2 Incidence of Treatment-Emergent Serious Adverse Events by System Organ Class, Preferred Term, and Age Group During Initial Treatment

TABLE 14.3_2.9.3 Incidence of Treatment-Emergent Drug-Related Adverse Events by System Organ Class, Preferred Term, and Age Group During Initial Treatment

TABLE 14.3_2.9.4 Incidence of Treatment-Emergent Drug-Related Serious Adverse Events by System Organ Class, Preferred Term, and Age Group During Initial Treatment

TABLE 14.3_2.9.5 Incidence of Treatment-Emergent Adverse Events Leading to Study Drug Discontinuation by System Organ Class, Preferred Term, and Age Group During Initial Treatment

TABLE 14.3_2.9.6 Incidence of Treatment-Emergent Adverse Events Leading to Death by System Organ Class, Preferred Term, and Age Group During Initial Treatment

TABLE 14.4_1.1 Chemistry: Observed and Change from Baseline During Initial Treatment

TABLE 14.4_1.2 Chemistry: Shift from Baseline to Maximum Post-Baseline NCI-CTCAE Grade During Initial Treatment

TABLE 14.4_2.1 Hematology: Observed and Change from Baseline During Initial Treatment

TABLE 14.4_2.2 Hematology: Shift from Baseline to Maximum Post-Baseline NCI-CTCAE Grade During Initial Treatment

TABLE 14.4_3.1 Coagulation: Observed and Change from Baseline During Initial Treatment

TABLE 14.4_3.2 Coagulation: Shift from Baseline to Maximum Post-Baseline NCI-CTCAE Grade During Initial Treatment

TABLE 14.4_4.1 Elevated AST, ALT, Total Bilirubin, and Alkaline Phosphatase During Initial Treatment

TABLE 14.3_5.1 Vital Signs During Initial Treatment

TABLE 14.3_5.2 Electrocardiogram During Initial Treatment

TABLE 14.3_6.1 Electrocardiogram: Summary of QTcF1 Interval During Initial Treatment

TABLE 14.3_7.1 Echocardiography: Pericardial Effusion During Initial Treatment

TABLE 14.3_8.1 ECOG Score: Shift from Baseline to Maximum Post-Baseline Value During Initial Treatment

TABLE 14.3_9.1 Concomitant Medications During Initial Treatment

TABLE 14.3_9.1.1 Serum Concentrations of ADC, Tab, D6.5, and SC16

TABLE 14.3_9.1.2 Serum Concentrations of ADC, Tab, D6.5, and SC16

FIGURE 14.2_1.1.1 Overall Survival

FIGURE 14.2_1.1.2 Overall Survival by DLL3 Score

FIGURE 14.2_1.2.1 Duration of Response

FIGURE 14.2_1.2.2 Duration of Response by DLL3 Score

FIGURE 14.2_1.3.1 Progression-Free Survival

FIGURE 14.2_1.3.2 Progression-Free Survival by DLL3 Score

FIGURE 14.2_2.1.1 Objective Response Rate by Central Radiology Review and by Subgroup (All Dosed Subjects)

FIGURE 14.2_2.1.2 Objective Response Rate by Central Radiology Review and by Subgroup (DLL3 High)

FIGURE 14.2_2.1.3 Objective Response Rate by Central Radiology Review and by Subgroup (DLL3 Positive)

FIGURE 14.2_2.1.4 Objective Response Rate by Central Radiology Review and by DLL3 (All Dosed Subjects)

FIGURE 14.2_2.2.1 Objective Response Rate by Investigator and by Subgroup (All Dosed Subjects)

FIGURE 14.2_2.2.2 Objective Response Rate by Investigator and by Subgroup (DLL3 High)

FIGURE 14.2_2.2.3 Objective Response Rate by Investigator and by Subgroup (DLL3 Positive)

FIGURE 14.2_ 2.2.4 Objective Response Rate by Investigator and by DLL3 (All Dosed Subjects)

FIGURE 14.2_ 2.3.1 Overall Response Rate by Central Radiology Review and by Subgroup (All Dosed Subjects)

FIGURE 14.2_ 2.3.2 Overall Response Rate by Central Radiology Review and by Subgroup (DLL3 High)

FIGURE 14.2_ 2.3.3 Overall Response Rate by Central Radiology Review and by Subgroup (DLL3 Positive)

FIGURE 14.2_ 2.4.1 Overall Response Rate by Investigator and by Subgroup (All Dosed Subjects)

FIGURE 14.2_ 2.4.2 Overall Response Rate by Investigator and by Subgroup (DLL3 High)

FIGURE 14.2_ 2.4.3 Overall Response Rate by Investigator and by Subgroup (DLL3 Positive)

FIGURE 14.2_ 2.5.1 Overall Survival by Subgroup

FIGURE 14.2_ 3.1 Maximum Percent Change in Target Lesion Measurement from Baseline for DLL3 High 3L per Investigator

FIGURE 14.2_ 3.2 Maximum Percent Change in Target Lesion Measurement from Baseline for DLL3 High 3L per Central Radiology Review

FIGURE 14.2_ 4.1 Percent Change in Target Lesion Measurement from Baseline for DLL3 High 3L with Best Overall Response of CR or PR per Investigator

FIGURE 14.2_ 4.2 Percent Change in Target Lesion Measurement from Baseline for DLL3 High 3L with Best Overall Response of CR or PR per Central Radiology Review

